## 3 Investigational plan

#### 3.1 Study design

This is a subject and investigator blinded, randomized, placebo-controlled, parallel-group, repeat-dose, multicenter, non-confirmatory study of CMK389 in chronic pulmonary sarcoidosis. This study will investigate the safety and efficacy of 10 mg/kg CMK389 administered intravenously (i.v.) every 4 weeks for a total of 4 doses, versus placebo (Figure 3-1). After obtaining signed informed consent, a screening epoch of 28 days will be used to assess subject eligibility. The population will consist of patients with biopsy-proven pulmonary sarcoidosis, in Scadding stages II, III, or IV as determined by the most recent chest

x-ray. A high resolution computed tomography (HRCT) scan (historical or performed at screening (**Day -70 to -43**)) will be reviewed to select subjects with minimal fibrosis (< 15% reticular markings on a volumetric basis). Eligible patients must be treated with 5-15 mg daily prednisone (or equivalent) and methotrexate or azathioprine for  $\geq 6$  months prior to screening. Hydroxychloroquine is allowed as background therapy but not required. Approximately 66 subjects will be randomized in a 1:1 ratio to receive CMK389 or placebo. Randomization will be stratified by prior sarcoidosis immunosuppressant therapy (azathioprine or methotrexate).

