## 4.1 Inclusion criteria

Subjects eligible for inclusion in this study must fulfill **all** of the following criteria:

- 1. Written informed consent must be obtained before any assessment is performed
- 2. Male and female subjects ages 18-75 years of age inclusive at screening
- Subjects must have a body mass index (BMI) at screening within the range of 18 46 kg/m^2. BMI = Body weight (kg) / [Height (m)]
- 4. Pulmonary Sarcoidosis present > 1 year prior to screening with a historical biopsy (from any organ or body part) confirming diagnosis prior to screening

- 5. Scadding stage II, III or IV as determined by the most recent chest x-ray obtained within 12 months prior to screening or at screening (confirmed by the investigator)
- 6. HRCT extent of fibrosis <20% (confirmed by the central imaging reader) on an HRCT obtained within 12 months prior to screening or at screening
- 7. Treatment with 5-15 mg/day prednisone (or prednisone oral equivalents) for
   ≥ 6 consecutive months prior to screening and with a minimum of 80% compliance with
   treatment each month as determined by the investigator.
- Co-medication with methotrexate or azathioprine for ≥ 6 months prior to screening and with a minimum of 80% compliance with treatment each month as determined by the investigator (Note: hydroxychloroquine is allowed as background therapy but not required)
- Able to perform reliable, reproducible pulmonary function test maneuvers per American Thoracic Society/European Respiratory Society (Culver et al 2017; Miller et al 2005; Graham et al 2017) guidelines
- 10. Able to communicate well with the investigator, to understand and comply with the requirements of the study

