## 8.8.2 High Resolution CT of Chest

An HRCT scan of the lung will be completed at screening to assess reticular pattern for the purpose of fulfilling eligibility criteria. The HRCT scans, without contrast agent, will be acquired at full inspiration according to parameters as listed in a separate imaging acquisition manual. Inclusion scans will be read by a central reader (expert radiologist) contracted through imaging vendor. The total whole body effective dose per subject from the HRCT scanning (excluding [F]FDG-PET/CT) will be maximally 4 mSv.

An historical HRCT obtained within 12 months from screening may also be sent to the central reader for over-read.

Refer to the Imaging Acquisition Guidelines and Imaging Investigator Site Operations Manual for HRCT details and requirements for historical HRCT.

The coded medical images will be used primarily for analysis as described in this protocol; however, the images may also be used for the development and evaluation of new analysis methods directly related to the area of research that this study covers. Incidental findings are beyond the scope of central imaging vendor. If an investigator/radiologist recognizes any incidental finding in the images during the course of conducting the clinical trial, the investigator should follow up as part of his/her duty of care to ensure the safety and wellbeing of the participant.

Commercially Confidential Information

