1.4 Study design and treatment

This is a subject and investigator-blinded, randomized, placebo-controlled, parallel group, repeat-dose, multicenter, non-confirmatory study of the safety and efficacy of CMK389 administered intravenously every 4 weeks for a total of 4 doses in chronic pulmonary sarcoidosis patients.

Approximately 66 patients will be randomized in a 1:1 ratio to receive either CMK389 or placebo. Randomization will be stratified by prior sarcoidosis immunosuppressant therapy (azathioprine or methotrexate). The expected total duration of participation for men and women of non-child bearing potential is approximately 38 weeks. For women of childbearing potential, the expected duration of participation is approximately 62 weeks.

Figure 1-1: Study design scheme

2 First interpretable results (FIR)

3 Interim analyses

Commercially Confidential Information

4 Statistical methods: Analysis sets

For all analysis sets, subjects will be analyzed according to the study treatment(s) received. In case(s) of miss-stratification, the real stratum will be used in the analysis.

The safety analysis set will include all subjects that received any study drug.

The PK analysis set will include all subjects with at least one available valid (i.e. not flagged for exclusion) PK concentration measurement, who received any study drug and with no protocol deviations with relevant impact on PK data.

The PD analysis set will include all subjects with available PD data and no protocol deviations with relevant impact on PD data. Also, data collected after a change of the background therapy not based on the CSE algorithm (see Section 3.1 of protocol) will be excluded from the analysis set if assessed as having a potentially relevant impact on PD data.

Table 4-1 Protocol deviation codes and analysis sets

Category Deviation code	Text description of deviation	Data exclusion
Subjects are excluded from all case of these PDs:	(safety) analysis in	Exclude subject completely from all (safety) analysis sets
INCL01	Deviation from inclusion criteria: Written informed consent was not obtained before any study assessment was performed	Yes
Subjects are excluded from Phthese PDs:	Canalysis in case of	Exclude subject from PK analysis set
INCL01	Deviation from inclusion criteria: Written informed consent was not obtained before any study assessment was performed	Yes

Subjects are excluded from PI these PDs:	Exclude subject from PD analysis set	

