INCL01	Deviation from inclusion criteria: Written informed consent was not obtained before any study assessment was performed	Yes
TRT01	Treatment deviation with impact on PD data	Yes
TRT02	Treatment deviation with impact on PD data from a timepoint onwards	Yes from a timepoint onwards
OTH01	Other deviation with impact on PD data	Yes
OTH02	Other deviation with impact on PD data from a timepoint onwards	Yes, from a timepoint onwards

Category Deviation code	Text description of deviation	Data exclusion
OTH04	Impact on spirometry and DLCO at a specific time point	Yes, at a specific timepoint only.
OTH12	Impact on spirometry at a specific time point	Yes, at a specific timepoint only.
OTH13	Impact on DLCO at a specific time point	Yes, at a specific timepoint only.
CMD02	Prohibited concomitant medication used with a relevant impact on efficacy endpoint	Yes, from a timepoint onwards
INCL04	Deviation from inclusion criteria: No biopsy proven pulmonary sarcoidosis diagnosed > 1 year prior to screening	Yes
INCL06	Deviation from inclusion criteria: HRCT <= 15% reticular volume at screening	Yes
EXCL05	Deviation from exclusion criteria: FVC < 50% at screening	Yes
EXCL06	Deviation from exclusion criteria: mMRC dyspnea scale >= 3 at screening	Yes
EXCL27	Deviation from exclusion criteria: deteriorated during Run-in	Yes

If updates to this table are needed, an amendment to the SAP needs to be implemented prior to DBL.

All DLCO related parameters will be excluded at specific visit only if the condition below is encountered: DLCO % change (absolute value) vs previous assessment > 35% or % change in alveolar volume vs previous assessment > 20%.

DLCO related parameters are: DLCO (absolute value and % predicted), ALVVOL (alveolar volume), DLCOHCCP (corrected by Hg), DLCOVA (/ volume), CPID (CPI = it includes DLCO).

5 Statistical methods for Pharmacokinetic (PK) parameters

All subjects within the PK analysis set will be included in the PK data analysis.

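### SAP Table 4-1 excludes subjects from the primary analysis set under an HRCT rule (15%, reticular volume) that does not match inclusion criterion 6 (fibrosis extent below 20%)

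*SAP*

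**What the plan says.** SAP Section 4 defines the set used for efficacy: "The PD analysis set will include all subjects with available PD data and no protocol deviations with relevant impact on PD data". SAP Section 6.1 and protocol Section 11.4.2 place the primary analysis of percent predicted FVC in that set. Table 4-1 then lists the deviations that lead to exclusion. Row INCL06 is described as "Deviation from inclusion criteria: HRCT <= 15% reticular volume at screening", with exclusion marked as a plain yes and no timepoint limit, so the whole subject is removed.

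The SAP states in Section 1.2 that it is based on protocol Amendment 8. In that protocol, Section 4.1, criterion 6 reads "HRCT extent of fibrosis <20% (confirmed by the central imaging reader"), on a scan from screening or the 12 months before it. The protocol summary repeats the 20% limit.

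Two other protocol passages describe the HRCT requirement differently. In Section 3.1 the scan "will be reviewed to select subjects with minimal fibrosis (< 15% reticular markings on a volumetric basis"). In Section 8.8.2 the scan is done "to assess reticular pattern for the purpose of fulfilling eligibility criteria".

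**The concern.** INCL06 decides who is in the primary analysis, and it disagrees with the criterion it codes in three respects.

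- **Threshold:** 15% in the row, 20% in criterion 6.
- **Measure:** reticular volume in the row, extent of fibrosis in criterion 6.
- **Direction:** the row appears to give the condition a patient should satisfy. The other inclusion rows give the failure, for example INCL04: "Deviation from inclusion criteria: No biopsy proven pulmonary sarcoidosis diagnosed > 1 year prior to screening". The exclusion rows also give the disqualifying condition, for example EXCL05: "Deviation from exclusion criteria: FVC < 50% at screening".

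Whoever codes deviations must therefore choose between 15% and 20%, and the protocol contains text for both. If the row's own figure is used, patients who were properly enrolled under criterion 6 leave the primary analysis. The cost would be precision, and under-representation of the more fibrotic part of the eligible population.

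**Working it through.** **Step 1. Sort patients under each reading.** This treats reticular volume and extent of fibrosis as one scale, which the documents do not establish.

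| Extent on HRCT | Criterion 6 | INCL06 read literally as the deviation | INCL06 read as a requirement not met |
|---|---|---|---|
| 15% or less | eligible | excluded | kept |
| above 15%, below 20% | eligible | kept | excluded |
| 20% or more | not eligible | kept | excluded |

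Neither reading reproduces criterion 6. The literal reading is wrong in both the first and the last line. The second reading gets the direction right but removes the eligible middle band. Section 3.1 does not match the row exactly either: it uses a strict inequality, so a patient at exactly 15% fails Section 3.1 but satisfies the row's condition.

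**Step 2. Reproduce the planned power.** Inputs from protocol Section 11.7: 28 per arm with Week 16 data, SD 9, true difference 5, success if the posterior probability is at least 90% with uninformative priors, type I error 10%. This corresponds to a one-sided test at 10%.

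- SE = 9 × √(2/28) = 2.405
- Normal approximation: 5/2.405 − 1.282 = 0.797, and Φ(0.797) = 0.787
- Noncentral t with 54 degrees of freedom: 0.783

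The protocol states approximately 80%, so the figure is reproduced. The recruitment figure also agrees: 66 × 0.85 = 56.1, or 28 per arm.

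**Step 3. Cost if 15% is applied as the requirement.** The share of patients in the middle band is not given, so 5%, 10% and 15% are assumed. Power is by noncentral t.

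| Assumed share | Dropped of 66 | Week 16 n per arm | SE | SE ratio to n = 28 | Power |
|---|---|---|---|---|---|
| 0% | 0 | 28 | 2.405 | 1 | 0.783 |
| 5% | 3.3 | 28 × 0.95 = 26.6 | 2.468 | 1.026 | 0.767 |
| 10% | 6.6 | 28 × 0.90 = 25.2 | 2.535 | 1.054 | 0.750 |
| 15% | 9.9 | 28 × 0.85 = 23.8 | 2.609 | 1.085 | 0.732 |

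Per dropped patient the loss is (78.3 − 76.7)/3.3 = 0.48 to (78.3 − 73.2)/9.9 = 0.52 percentage point of power. The normal approximation at n = 23.8 gives 0.737, in line with the table.

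**Step 4. Cost if deviations are coded against criterion 6.** Only patients who fail criterion 6 are removed, no eligible patient is lost, and the planned n is unaffected.

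**The case against.** The best defence is that the protocol already settles which rule governs. Section 4 requires every subject to meet the listed eligibility criteria and bars investigators from adding others, and Section 8.4.5 repeats this. Section 3.1 is design narrative, and Section 8.8.2 merely refers to the eligibility criteria. A patient between 15% and 20% who meets criterion 6 has no inclusion deviation, and without a deviation the PD set definition removes nobody. The row carries the number 06 and is labelled as a deviation from the inclusion criteria. Section 10.1 has monitors verify adherence to those criteria, and Section 10.3 has deviations determined before lock. On this view Table 4-1 is shorthand, as its other abbreviated descriptions suggest.

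The direction argument can also be narrowed. For an exclusion criterion, citing the criterion and stating the failure are the same thing, so EXCL05, EXCL06 and EXCL27 cannot show which convention the table follows. Only INCL01 and INCL04 can, and a label followed by the criterion breached is a natural way to read INCL06.

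Much of this stands. Coding against criterion 6 is the likely route, and nobody is likely to apply the literal reading, which would exclude the patients the trial selects for. But the defence resolves the direction and leaves the threshold open. Sections 4 and 8.4.5 govern enrolment and do not correct the SAP row, which is a separate rule for the analysis set. Its 15% is not an isolated slip, since Section 3.1 carries the same figure. No passage states outright what triggers INCL06.

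**Conclusion.** The concern holds: the row is wrong as written. Confidence is high for the mismatch, which is plain in the current text and is not explained by redaction or by superseded wording. Loss of patients is possible but not shown.

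The likely effect is zero. If 15% were applied as the requirement, the cost is about half a percentage point of power per eligible patient dropped. At an assumed 15% share, that means about 10 of 66 patients, power of about 73% against 78%, and a standard error about 8% larger. These figures rest on the assumed share and on treating the two HRCT measures as one scale. HRCT eligibility is read before randomisation and the rule applies to both arms, so it does not by itself bias the treatment comparison.

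It should be fixed, because membership of the primary analysis set should not depend on interpretation when deviations are coded.

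**What to change.** Reword INCL06 as failure of inclusion criterion 6. As that criterion stands, this means a centrally read HRCT extent of fibrosis of 20% or more. Naming the criterion by number keeps the row aligned with whatever criterion 6 says.

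Reconcile protocol Section 3.1 and the reticular-pattern wording of Section 8.8.2 with criterion 6. No view is taken here on which threshold or measure is clinically right, only that one must govern.

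The SAP change is one table row, by the route the SAP already sets out: "If updates to this table are needed, an amendment to the SAP needs to be implemented prior to DBL". Changing Section 3.1 or 8.8.2 needs a written protocol amendment with the approvals in Section 13.1, which can be bundled with another amendment. The SAP row need not wait for it. No new data are needed and the model does not change.

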5.1 Variables

The following pharmacokinetic parameters will be determined:

- CMK389 plasma concentration.
- Commercially Confidential Information

5.2 Descriptive analyses

CMK989 plasma concentration data will be listed by subject and visit/sampling time point. Descriptive summary statistics will be provided by visit/sampling time point. Summary statistics will include mean (arithmetic and geometric), SD, CV (arithmetic and geometric), median, minimum and maximum.

Commercially Confidential Information

The geometric mean will not be reported if the dataset includes zero values.

Graphical methods will be employed to show mean and individual concentration-time profiles.

6 Statistical methods for Pharmacodynamic (PD) parameters

All subjects within the PD analysis set will be included in the PD data analysis.

6.1 Primary objective

To assess the efficacy of CMK389 in subjects with chronic pulmonary sarcoidosis.

It will be estimated in the PD analysis set and considering the FVC (% of predicted) change from baseline at week 16, irrespective of the role played by the steroid dose ('treatment policy' approach) and managing missing values according to an hypothetical approach. Therefore, the primary analysis will estimate the treatment effect if everyone would have been able to finish the treatment period. The difference in the model based mean in the CMK389 vs placebo arm will be used to estimate the effect.

6.1.1 Variables

The primary variable will be the change from baseline in percent predicted FVC at Week 16. The FVC is measured at screening, day 1, week 4, week 8, week 12, and week 16. Baseline is defined as day 1.

For the primary analysis, the only data quality condition affecting data inclusion to the analysis will be that the number of accepted tests is greater than zero. No other flags related to quality

will lead to an exclusion of records Also, the main efficacy analysis will exclude all the data collected after a steroid dose increase NOT driven by the algorithm.

These cases will be detected programmatically and will be reconciled by manual checks. Should it become not feasible to detect all cases programmatically, then the team will release an excel file with the list of events and dates. According to each case, efficacy data will be excluded at a specific visit, or will be excluded from a timepoint onwards.

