## Run-in Epoch

[figure not shown]
A 6-week run-in epoch will commence on **Day -42**. First, eligible patients will discontinue methotrexate and azathioprine. Hydroxychloroguine will be allowed to continue as background therapy. Then, on **Day -28** (2 weeks after discontinuation of methotrexate or azathioprine), patients will undergo a full safety assessment, a "Clinical Status Evaluation (CSE)", and enter into a steroid (prednisone or equivalent; see Table 17-1-Appendix 3) titration algorithm. CSE will consist of a 6-minute walk test, spirometry assessments, and an assessment of dyspnea (Modified Medical Research Council [mMRC] breathlessness scale). The CSE serves as an additional safety evaluation and will serve to establish the patient's current clinical status (Clinical Status Determination [CSD]) as compared to their status at Day -42 (Figure 3-2). The CSE will be performed at each subsequent visit, prior to the titration of steroids, and the CSD will guide selection of the next dose of steroids (Figure 3-3). Steroid titration will continue through the run-in epoch: and steroid titration will also continue through the treatment epoch. Patients with CSD of "improved" or "stable" will decrease steroid dose by 1-step on the dosing scale (Figure 3-4). (Note: To prevent Addisonian crisis, steroids will not be tapered below a physiologic dose (2.5 mg/day); and steroid tapering will follow a very slow regimen, as per protocol – i.e., modest decreases in dose, no more frequent than every four weeks). Patients with CSD of "deteriorating" will be ineligible to continue the study (if "deteriorating" is determined during the run-in epoch); or they will increase their steroid dose by 1-step (if "deteriorating" is determined during the treatment epoch). [ $^{18}$ F]-FDG PET/CT will be performed prior to the first dose (**Day -2 (± 1**)) and again at the end of the treatment epoch (**Day 113**).

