# Figure 3-2 Clinical Status Evaluation (CSE) and Clinical Status Determination (CSD)

	Clinical Status Evaluation (CSE)											
D		Change since Day -42 (V101)										
Parameters	Better	Same	Worse									
6MWT	↑ 50m	$\Delta = \pm (<50) \mathrm{m}$	↓ 50m									
FVC	+10% relative $\Delta$	-15% < relative $\Delta$ < +10%	-15% relative $\Delta$									
FEV1	+10% relative $\Delta$	-15% < relative $\Delta$ < +10%	-15% relative $\Delta$									
MMRC dyspnea score	-1 point	No change	+1 point									

Clinical Status	Improved	Stable	Deteriorating
Determination	3 or more parameters	Does not meet criteria for	2 or more parameters "Worse"
(CSD)	"Better"	"Improved" or "Deteriorating"	or $\Delta$ MMRC is $\geq$ 2 points

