### Highly effective contraception methods include:

- Total abstinence (when this is in line with the preferred and usual lifestyle of the subject. Periodic abstinence (e.g. calendar, ovulation, symptothermal, post-ovulation methods) and withdrawal are not acceptable methods of contraception
- Male/female sterilization
- Use of oral, injected or implanted hormonal methods of contraception or placement of an intrauterine device (IUD) or intrauterine system (IUS) or other forms of hormonal contraception that have comparable efficacy (failure rate <1%), for example hormone vaginal ring or transdermal hormone contraception

In case of use of oral contraception, women should be stable on the same pill for a minimum of 3 months before taking investigational drug.

- 22. Other history or current diagnosis of ECG abnormalities not due to cardiac sarcoidosis at screening as determined by the investigator and based on the totality of the safety information to indicate significant safety risk. The following should be considered by the investigator in guiding the determination as part of the overall assessment, but should not be considered in isolation:
  - PR > 200 msec
  - QRS complex > 120 msec
  - QTcF > 450 msec (males)
  - QTcF > 460 msec (females)
- 23. Concomitant clinically significant cardiac arrhythmias, e.g. sustained ventricular tachycardia, and clinically significant second or third degree AV block without a pacemaker
- 24. Significant illness which has not resolved within two weeks prior to initial dosing
- 25. Donation or loss of 400 mL or more of blood within eight weeks prior to initial dosing, or longer if required by local regulation
- 26. Any surgical or medical condition which might significantly alter the absorption, distribution, metabolism, or excretion of drugs, or which may jeopardize the subject in case of participation in the study. The investigator should make this determination in consultation with the sponsor and in consideration of the subject's medical history and/or clinical or laboratory evidence.
- 27. Clinical Status Determination (CSD) of "deteriorating" at Day-28 (V102) or Day 1 (V201)

- 28. A diagnosis of Lofgren's syndrome
- 29. History of pancreatitis
- 30. Other pulmonary disease (i.e., asthma, bronchiectasis, COPD, etc.) unrelated to sarcoid as determined by the investigator
- 31. Active drug or alcohol abuse (as defined by the investigator) within 3 months prior to screening.

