6.1.3 Statistical model, assumptions and hypotheses

The change from baseline in percent predicted FVC will be analyzed using a Bayesian model for repeated measurements including data collected at weeks 4, 8, 12 and 16. The model will investigate effects for treatment by time (included as a class variable) interaction, baseline percent predicted FVC by time interaction and will include the covariates prior sarcoidosis immunosuppressant therapy (stratification factor) and baseline prednisone dose. Uninformative priors for all the parameters will be utilized to obtain the posterior estimates. The correlation among the repeated measures collected on the same subject will be assessed via unstructured covariance matrix. The stratification factor may be removed in case of strata with low sample sizes impacting on the model fit. Baseline FVC and prednisone will be centered and standardized before used in the model

Commercially Confidential Information

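### The primary model adjusts for one FVC taken during the run-in taper; adding the Day -42 FVC already collected is a cheap change that may gain precision

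*SAP*

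**What the plan says.** On the FVC visits, SAP 6.1.1 says "The FVC is measured at screening, day 1, week 4, week 8, week 12, and week 16", and then "Baseline is defined as day 1". The model in SAP 6.1.3 is fitted "including data collected at weeks 4, 8, 12 and 16". Apart from treatment by time, its terms are "baseline percent predicted FVC by time interaction and will include the covariates prior sarcoidosis immunosuppressant therapy (stratification factor) and baseline prednisone dose". Protocol 11.4.2 gives the same set of terms. No FVC taken before Day 1 enters the model.

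The protocol collects more than this. Table 8-1 marks spirometry at screening, V101 (Day -42), V102 (Day -28), Day 1 and each four-weekly visit to Week 16. In Protocol 3.1, "CSE will consist of a 6-minute walk test, spirometry assessments, and an assessment of dyspnea". The change column of Figure 3-2 is headed "Change since Day -42 (V101", so the Day -42 FVC is the reference for the FVC rating at every visit where clinical status is determined. Exclusion criterion 27 requires that determination at Day -28 and at Day 1, before randomisation.

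**The concern.** Day 1 is one reading in a period of deliberate change. Methotrexate or azathioprine stops from Day -42, and the first steroid step comes at Day -28. The Day 1 FVC is taken after both and before the Day 1 step. Under Figure 3-2 a relative FVC fall of less than 15% since Day -42 is still rated as unchanged. A larger fall in FVC alone does not make a patient deteriorating, because that needs two worse parameters or a dyspnea change of at least 2 points. Patients can therefore reach Day 1 with the same FVC after quite different run-in courses. SAP 6.1.1 accepts a reading with any number of accepted tests above zero, so a noisy Day 1 value counts fully.

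If the Day -42 value predicts Week 16 FVC beyond what Day 1 tells us, that information stays in the residual variance, and a chance imbalance in run-in decline between two arms of about 28 is not adjusted for. There is some reason to expect a link. Steroid dosing during treatment is guided by change since Day -42, and the primary analysis keeps FVC measured after algorithm-driven steroid changes. FVC is only one of four parameters, so this says nothing about the size.

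**Working it through.** **Inputs from Protocol 11.7:** 28 evaluable patients per arm, SD 9, true difference 5, success if the posterior probability is at least 90%, type I error 10%, about 66 randomised with 15% dropout.

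**The plan's own figure.** With uninformative priors the criterion acts as a one-sided 10% test.
- SE = 9 × √(2/28) = 2.405, and 5/2.405 = 2.079.
- Power = Φ(2.079 − 1.282) = 78.7%, against approximately 80% stated.
- 56/0.85 = 65.9, so 66 randomised.

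The stated design is reproduced.

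**Effect of a second baseline value.** Let r be the partial correlation of Day -42 FVC with Week 16 FVC, given Day 1 FVC. Adding Day -42 multiplies the residual variance by 1 − r². Power becomes Φ(2.079/√(1 − r²) − 1.282). SD 9 is read here as the residual SD given Day 1 FVC; the protocol does not say which SD it is. No correlation is given in either document, so all three cases below are assumptions.

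1. *Day 1 carries all the information (r = 0).* The variance does not fall. Allowing for one extra coefficient by a variance factor of about 52/51, power is about 78.1%.

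2. *Correlation decays with time.* Take 0.85 for Day -42 with Day 1 and for Day 1 with Week 16, and c for Day -42 with Week 16. Then r = (c − 0.85²)/(1 − 0.85²) = (c − 0.7225)/0.2775.

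| c | r | variance factor |
|---|---|---|
| 0.7225 | 0 | 1.00 |
| 0.75 | 0.099 | 0.990 |
| 0.78 | 0.207 | 0.957 |
| 0.80 | 0.279 | 0.922 |
| 0.82 | 0.351 | 0.877 |

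For c from 0.75 to 0.82 the variance falls by about 1-12%. Power is Φ(2.079/√0.990 − 1.282) = 79.0% to Φ(2.079/√0.877 − 1.282) = 82.6%.

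3. *Equal correlation ρ between all three visits.* The factor is (1 + 2ρ)/(1 + ρ)².

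| ρ | variance factor | power |
|---|---|---|
| 0.7 | 2.4/2.89 = 0.830 | 84.1% |
| 0.8 | 2.6/3.24 = 0.802 | 85.1% |
| 0.9 | 2.8/3.61 = 0.776 | 86.0% |

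The powers in cases 2 and 3 are before the cost of the extra coefficient, which is about half a point.

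**The case against.** The strongest reply is that nothing in the primary analysis is wrong. Day 1 is the last pre-dose value, both documents define it as baseline, and randomisation protects the comparison. A patient who dips in the run-in and then drifts back is equally likely in either arm, so the effect is on variance only. This stands. A reader might infer bias, or a misstated power, from a single baseline taken during a taper; the documents support neither.

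A reader might also infer that the SAP discards the run-in FVC altogether. It does not. SAP 6.1.2 lists FVC by visit, and SAP 6.2.2 summarises the clinical status ratings, which are measured against Day -42, by treatment and visit. The gap is in the model.

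The gain may be nil. It is tempting to quote the equal-correlation case as the expected benefit, equivalent to 28/0.830 = 33.7 up to 28/0.776 = 36.1 patients per arm. But a treatment withdrawal and a steroid step lie between Day -42 and Day 1, so equal correlation with Week 16 cannot be taken for granted. Excluding deteriorating patients before randomisation also truncates the run-in change, which may alter the correlation.

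The change is also not quite free. The covariates are set in Protocol 11.4.2, so editing the SAP alone would make the two documents differ. Entering Day -42 by time would add four coefficients to a model with an unstructured covariance, for which both documents already foresee fitting problems. An unusable Day -42 reading would leave a missing covariate. These points shape the fix; they do not remove the case for it.

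**Conclusion.** The point holds as a low-cost improvement. The model conditions on one FVC taken mid-taper and leaves out a pre-randomisation FVC that the design requires. The Day 1 analysis remains valid and unbiased, and the stated power is reproduced.

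The size rests wholly on an assumed correlation: from no gain, with about 0.6 of a power point lost (78.7% to 78.1%), through a 1-12% cut in residual variance under decay, to 17-22% and power of about 84-86% under equal correlation of 0.7-0.9. The last is the favourable end of the range. With 28 evaluable patients per arm, the small possible loss is worth accepting. The incomplete visit list in SAP 6.1.1 changes no result, because SAP 6.1.3 states the modelled weeks separately.

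**What to change.** Before unblinding:

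- In SAP 6.1.3, add Day -42 (V101) percent predicted FVC, centred and standardised like the Day 1 value, as one main-effect covariate. Keep Day 1 as baseline.
- Align Protocol 11.4.2, or record the addition as a change from it.
- State that an unusable Day -42 value is replaced without regard to treatment arm, for example by the screening FVC or by mean or regression imputation from pre-randomisation data, so that no patient drops out of the primary model.
- Allow the term to be dropped if the model does not converge.
- Reconcile the visit list in SAP 6.1.1 with Table 8-1 by adding Day -42 and Day -28.

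The same term for FEV1 and 6MWD in SAP 6.2.3 is optional.

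The cost is a few sentences across the two documents, one model term and one degree of freedom, with possibly no gain. No new data are needed, and neither the baseline nor the estimand changes.
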